APPENDIX 9: ALOPECIA IMPACT ASSESSMENT

Alopecia Impact Assessment (AIA)

Instructions: The following questions are about your alopecia. For each question, please select the box (☒) below the number that best describes your experience with alopecia during the past seven days. There are no right or wrong answers.

1. During the past seven days, how bothersome was it to cover your hair loss (e.g., wearing a wig, using makeup to fill in eyebrows, wearing hats)?	Not at all bothersome										Extremely bothersome	
	0	1	2	3	4	5	6	7	8	9	10	
												
2. During the past seven days, how worried were you about your appearance due to your hair loss?	Not at all worried										Extremely worried	
	0	1	2	3	4	5	6	7	8	9	10	
												
3. During the past seven days, how sad did you feel due to your hair loss?	Not at all sad										Extremely sad	
	0	1	2	3	4	5	6	7	8	9	10	
												
4. During the past seven days, how much did your hair loss impact your confidence?	Not at all impacted										Extremely impacted	
	0	1	2	3	4	5	6	7	8	9	10	
												
5. During the past seven days, how self-conscious did you feel due to your hair loss (e.g., feeling uncomfortable with hair/hair loss in public)?	Not at all self-conscious										Extremely self-conscious	
	0	1	2	3	4	5	6	7	8	9	10	

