												
6. During the past seven days, how embarrassed did you feel due to your hair loss (e.g., feeling awkward about, or ashamed of, hair loss)?	Not at all embarrassed										Extremely embarrassed	
	0	1	2	3	4	5	6	7	8	9	10	
												

7. During the past seven days, how unattractive did you feel due to your hair loss?	Did not feel unattractive at all										Felt extremely unattractive	
	0	1	2	3	4	5	6	7	8	9	10	
												
8. During the past seven days, how much did your hair loss limit your social activities (e.g., spending time with friends, going to a social event)?	Not at all limited										Extremely limited	
	0	1	2	3	4	5	6	7	8	9	10	
												
9. During the past seven days, how much did your hair loss limit your physical activities (e.g., going to the gym, swimming, playing sports)?	Not at all limited										Extremely limited	
	0	1	2	3	4	5	6	7	8	9	10	
												
10. During the past seven days, how bothersome was unwanted or negative attention from others due to your hair loss (e.g., staring, questions)?	Not at all bothersome										Extremely bothersome	
	0	1	2	3	4	5	6	7	8	9	10	

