												
11. During the past seven days, how bothersome was your experience of getting sweat in your eyes due to your hair loss?	Not at all bothersome										Extremely bothersome	
	0	1	2	3	4	5	6	7	8	9	10	
												
12. During the past seven days, how bothersome was your experience of getting debris in your eyes due to your hair loss?	Not at all bothersome										Extremely bothersome	
	0	1	2	3	4	5	6	7	8	9	10	
												
13. During the past seven days, how bothersome was your experience getting debris in your nose due to your hair loss?	Not at all bothersome										Extremely bothersome	
	0	1	2	3	4	5	6	7	8	9	10	
												

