The AIA-PRO consists of 13 questions each rated on a scale of 1 to 10 and mean total score. The mean total score is taken as the average of the 13 items. If any of the items is missing the mean total score will not be calculated. Descriptive statistics for actual and change from baseline for the mean total score and each individual item will be presented.

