### Other Efficacy

40. Table 14.2.7.1 Subject Global Impression of Treatment Satisfaction (SGITS) over Time, ITT Population
41. Table 14.2.8.1 Shift from Baseline to Week 24 in Hair Pull Test Results - Dislodged Hairs and Broken Hairs, ITT Population
42. Table 14.2.9.1 Summary of DLQI Score and Change from Baseline by Visit, ITT Population
43. Table 14.2.9.2 Analysis of Change from Baseline in DLQI Total Score over Time, ITT Population
44. Table 14.2.10.1 AIA-PRO, Total Score, ITT Population
45. Table 14.2.10.2 AIA-PRO, Cover Hair Loss, ITT Population
46. Table 14.2.10.3 AIA-PRO, Worried about Appearance, ITT Population
47. Table 14.2.10.4 AIA-PRO, Sad Due to Hair Loss, ITT Population
48. Table 14.2.10.5 AIA-PRO, Confidence, ITT Population
49. Table 14.2.10.6 AIA-PRO, Self-Conscious, ITT Population
50. Table 14.2.10.7 AIA-PRO, Embarrassed, ITT Population
51. Table 14.2.10.8 AIA-PRO, Unattractive, ITT Population
52. Table 14.2.10.9 AIA-PRO, Limit Social Activity, ITT Population
53. Table 14.2.10.10 AIA-PRO, Unwanted Attention, ITT Population
54. Table 14.2.10.11 AIA-PRO, Sweat in Eyes, ITT Population
55. Table 14.2.10.12 AIA-PRO, Debris in Eyes, ITT Population
56. Table 14.2.10.13 AIA-PRO, Debris in Nose, ITT Population

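### SAP 5.2.5 gives the Alopecia Impact Assessment items the wrong range, the table list leaves out item 9, and one blank item voids the total with no stated fallback

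*SAP*

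**What the plan says.** SAP 5.2.5 defines the score in three statements. On the items: "The AIA-PRO consists of 13 questions each rated on a scale of 1 to 10 and mean total score". On the total: "The mean total score is taken as the average of the 13 items". On missing items: "If any of the items is missing the mean total score will not be calculated". It then plans descriptive statistics, actual and change from baseline, for the mean total and for each item. It names no test for this instrument.

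The form is in protocol Appendix 9. Each of its 13 items has the response boxes "0 1 2 3 4 5 6 7 8 9 10". Item 9 asks "how much did your hair loss limit your physical activities".

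The table list in SAP 8.1, under Other Efficacy, has one table for the total (14.2.10.1) and item tables 14.2.10.2 to 14.2.10.13. The item 8 entry is "Table 14.2.10.9 AIA-PRO, Limit Social Activity, ITT Population"; the next entry, 14.2.10.10, is for unwanted attention, which is item 10. Data listing 16 in the same section covers the scale items and the total.

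SAP 3.3.4 applies LOCF to missing clinical assessments in general. It has no rule for single questionnaire items. SAP 6 states that the SAP's analyses are consistent with the protocol.

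**The concern.** Two of the three points are contradictions on the page. The SAP's scale excludes an answer that the form offers, and the table list does not deliver what 5.2.5 promises. The range matters somewhat beyond tidiness: the AIA is newly developed, score interpretation is a secondary objective of the trial, and a separate psychometric plan will use the same scores. The two plans should describe the same scale.

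The third point is a choice of rule. With 13 items, a small blank rate per item becomes a much larger rate of missing totals. Blanks are foreseeable. Item 1 asks "how bothersome was it to cover your hair loss (e.g., wearing a wig, using makeup to fill in eyebrows, wearing hats", and item 9 concerns physical activities, yet the form has no box for a question that does not apply. The DLQI in the same trial offers a not-relevant response for most of its questions, including sport, and the SAP scores it 0. The AIA has neither that option nor a fallback in scoring. At stake are precision on this secondary endpoint and its coverage of the ITT population, to which protocol 11.4.2 commits all secondary efficacy analyses.

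**Working it through.** **Range.** The plan's own figure here is the item range, 1 to 10. It does not reproduce from the form, which gives 0 to 10.

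- Mean of 13 items: 0 to 10 from the form, against 1 to 10 as the SAP has it.
- Change from baseline: -10 to +10, against -9 to +9.
- The SAP specifies no recoding. Raw values averaged as recorded give the right mean and change. A uniform shift of all items would cancel in the change.

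**Item tables.** Form items 1 to 8 match Tables 14.2.10.2 to 14.2.10.9, and items 10 to 13 match Tables 14.2.10.10 to 14.2.10.13. That is 8 + 4 = 12 tables for 13 items. Only item 9 is unmatched.

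**Voided totals.** Inputs: 13 items and the any-blank rule (SAP 5.2.5); collection at baseline and Weeks 4, 12 and 24 (protocol 8.3.2); 40 subjects per arm (SAP 3.1). The per-item blank rate p is an assumption, shown over a range, and items are taken as independent within a visit. Dropout is not counted.

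- Total void at one visit: v = 1 - (1 - p)^13.
- Change score lost if the same subjects skip at both visits: v.
- Change score lost if LOCF carries an earlier post-baseline total forward and visits are independent: 1 - (1 - v)(1 - v^3). Baseline must be complete, together with at least one of the three post-baseline totals.
- Change score lost if visits are independent and LOCF does not apply: 1 - (1 - p)^26.

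| p | Void at one visit (= lost if the same subjects skip) | Lost, LOCF applies | Lost, independent visits, no LOCF |
|---|---|---|---|
| 0.5% | 6.3% | 6.3% | 12.2% |
| 1% | 12.2% | 12.4% | 23.0% |
| 2% | 23.1% | 24.0% | 40.9% |

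At 1%: v = 1 - 0.99^13 = 0.1225; with LOCF, 1 - 0.8775 x (1 - 0.1225^3) = 0.124; without it, 1 - 0.99^26 = 0.230. In an arm of 40 these are 40 x 0.1225 = 4.9 subjects at the low end and 40 x 0.230 = 9.2 at the high end.

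**Why baseline sets the floor.** SAP 3.3.6 takes baseline as the last non-missing value before study medication. The AIA is first collected at Visit 2, so nothing earlier can be carried forward. A blank there removes that subject's change in the total at every visit.

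**Whether LOCF applies afterwards.** SAP 3.3.4 could be read either way for a questionnaire that was completed but whose total was voided. The AIA table titles carry no LOCF label, whereas the SALT analysis tables do. That is suggestive only, since other tables also lack the label.

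**The case against.** The strongest reply is that little follows from any of this. The range is a wording slip: the SAP defines no truncation or range check for the AIA, so zeros enter the average correctly. Item 9 remains in the 13-item mean and in Listing 16; only a summary table is missing, from a list headed as proposed. The complete-item rule is explicit and prespecified, and prorating an instrument whose properties are still under evaluation is a judgement. Subjects answer during the visit on staff instruction, so blanks may be noticed. The low anchors of items 1 and 9 are usable by someone who does not cover the hair loss or play sport. Most of this stands, and it limits the point to a minor one. It does not remove the two contradictions, the unrecoverable baseline blank or the silence on LOCF.

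A reader might infer more than the documents support:

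- *The endpoint will be computed wrongly, because zeros will be queried and set to missing.* Protocol 12.3 mentions edit checks but none for the AIA range.
- *Item 9 is dropped from the outputs.* It is absent from the summary tables only.
- *The lost subjects are those with milder or uncovered disease, or with intact brows and lashes.* No entry criterion or data in the documents support this, and the extension expects some subjects with eyebrow loss.
- *About a quarter of change scores will be lost.* The 23% needs a 1% blank rate, independence across visits and no LOCF. If items are skipped because they do not apply, the same subjects would tend to skip both times, which points to about 12%.

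**Conclusion.** The point holds as a minor one. SAP 5.2.5 contradicts the form on the item range, and SAP 8.1 contradicts 5.2.5 on item 9; neither depends on any assumption. The any-blank rule can lose change scores, but the size is conditional because the documents give no blank rate. At an assumed 1% per item, with items independent within a visit, the loss is about 12% if the same subjects skip at both visits or if LOCF applies. It reaches 23% if blanks are independent across visits and LOCF does not apply. Blanks clustered in a few subjects would lose fewer. The primary analysis and its alpha are untouched, since the AIA is a separate, descriptive secondary endpoint.

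**What to change.** 1. In SAP 5.2.5, state the item range and the mean-total range as 0 to 10.
2. In SAP 8.1, add the summary table for item 9, physical activities.
3. Compute the mean total from the answered items when a prespecified minimum is met, otherwise set it to missing, and keep the complete-13-item version as a sensitivity summary. At least 10 of 13 is one reasonable minimum; it is a judgement and should be aligned with the separate psychometric plan.
4. State whether LOCF applies to a missing AIA total, and label the AIA tables accordingly.

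The cost is a few sentences, one item table and one sensitivity summary. The small downside is that prorated totals average slightly different content across subjects, which the complete-item summary would show.

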#### **5.2.6. Other Efficacy**

Results from the hair pull test at scheduled visits will be summarized. The summary will show the shift relative to baseline in the categories of dislodged hairs and broken hairs at each post-baseline analysis visit.

#### **5.2.7. Subset Analyses**

##### Subgroups of Baseline SALT score group ( $< 50$ , $\geq 50$ )

The primary analysis of the percent change in SALT score over time, the analysis of percent change in ALODEX score over time, and all planned responder-type analyses will be repeated in

each subgroup. For these analyses, the baseline SALT score group will be removed from the planned MMRM model and logistic regression model.

#### Subgroup of subjects who applied Whole Scalp Treatment

This subset will consist of all subjects who indicated on the End of Blinded Treatment page of the eCRF that the whole scalp is treated twice per day. The primary efficacy analysis of the percent change in SALT score will be repeated in this subset.

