 - Clarified that the proportion of subjects achieving $\geq 50\%$ hair regrowth compared with baseline will be analyzed using a separate model for SALT and for ALODEX scores
- Updating the number of sites from approximately 20 to 27.

Protocol Version 6.0 dated 08AUG2018 was amended to change the area of the study medication application from the areas of the scalp with patchy alopecia areata including a $\frac{1}{2}$ inch margin around the patchy areas to application to the entire scalp. Subjects will apply up to 4-mLs, twice-daily; once in the morning and approximately 12 hours.

Protocol Version 7.0 (Amendment 6, dated 10AUG2018) was amended to allow inclusion of subjects ≥ 12 years old (previously ≥ 18 years old).

Administrative Letter #3 dated 28AUG2018 provided the previously approved study medication application instructions for use when applying drug to the patchy areas only. Administrative Letter #4 dated 06SEP2018 clarified the study medication allocation instructions for subjects < 18 years of age. Administrative Letter #5 dated 14SEP2018 updated the title to include adolescents.

Protocol Version 8.0 (Amendment 7, dated 26SEP2018) allowed subjects who complete the double-blind portion of the study to have the option of enrolling into a long-term open-label extension (OLE) period to apply ATI-50002 Topical Solution 0.46%. The purpose is to allow subjects who may have received placebo an opportunity to apply active treatment and subjects on active treatment to extend the treatment period. Amendments 1-8 have been incorporated into the final protocol dated 09APR2019

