- Change from baseline in the subject reported Alopecia Impact Assessment (AIA) at Week 24 (Visit 10)
- Subject Global Impression of Treatment Satisfaction at Week 24 (Visit 10)
- Change in Dermatology Life Quality Index (DLQI) total score between Baseline and Week 24 (Visit 10)
- Global Impression of Change (Clinician and Subject) at Week 24 (Visit 10)

Exploratory:

- At select clinical sites, the change from baseline in the effects of ATI-50002 induced Janus kinase (JAK) 1/3 inhibition on the ALADIN scores, peribulbar infiltrate and other inflammatory biomarkers

Safety:

- Safety variables to be assessed include: adverse events, clinical laboratory tests (hematology, clinical chemistry, and urinalysis), vital sign measurements (systolic and diastolic blood pressures, respiration rate, heart rate, and oral body temperature), and electrocardiograms.

Long-term:

- Safety variables, efficacy variables [(change from baseline in SALT, ALODEX at long-term visits), (change from baseline in AAA-SR, AAA-CR, SGITS)].

Study Medication Administration

Subjects will apply up to a maximum of 4 mL of topical solution to the entire scalp twice-daily as directed.

Prior to amendment 5, subjects were instructed to treat patches of active alopecia areata and not the entire scalp. Subjects who signed the ICF prior to amendment 5 and do not consent to twice-daily applications to the entire scalp may continue in the study. These subjects should be given the option to

apply the study medication to the entire scalp at night only, and the patchy areas during the day or to the patchy alopecia areas and a $\frac{1}{2}$ " margin around the areas twice-daily. The areas being treated must be identified in the source documentation and the eCRF as; patchy areas only twice-daily, entire scalp twice-daily or patchy areas only once-daily, and entire scalp once-daily.

In the OLE, in addition to applying study medication to the entire scalp twice-daily (or patchy areas with a $\frac{1}{2}$ " margin if the subject did not agree to apply to the entire scalp) subjects with eyebrow loss will be allowed to apply a thin film of study medication twice-daily to the affected eyebrow(s) as directed.

Statistical Methods

The primary analysis will be conducted when all subjects have completed the double-blind period.

Sample Size/ Power Calculations

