Subjects who signed the ICF prior to amendment 5 and do not consent to twice-daily applications to the entire scalp may continue in the study. These subjects should be given the option to apply the study medication to the entire scalp at night only, and the patchy areas during the day or to the patchy alopecia areas and a $\frac{1}{2}$ " margin around the areas twice-daily. The areas being treated must be identified in the source documentation and the eCRF as:

- patchy areas only twice-daily,
- entire scalp twice-daily or
- patchy areas only once-daily, and entire scalp once-daily.

If the subject develops a new patch of hair loss during the study (e.g. areas of the scalp with active shedding) the investigator will instruct the subject to treat the new area of hair loss. The investigator must incorporate the new area of hair loss, once it is clinically evident, into the SALT and ALODEX score assessments. The investigator must determine if additional study medication is required to cover the new patchy area(s) and if applicable, document the new amount of study medication to be applied in the source documents and on the subject instruction sheet. If a subject believes symptoms indicate a new area of impending hair loss, but no hair loss is clinically apparent, the area will be noted in the source document, but will not be treated or included in SALT or ALODEX assessment until clinically apparent as either thinned or alopecic patch. New patches of hair loss that develop during the study are not considered an adverse event.

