### **3.3. HANDLING OF DATA**

#### **3.3.1. Strata and Covariates**

The baseline SALT score group (<50, >=50) will be used a stratum in the planned primary efficacy models. The strata will not be used in the subset analyses.

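### The whole-scalp subset is defined by the regimen reported at the end of treatment, so for subjects randomised before Amendment 5 membership is a post-randomisation choice and late switchers count as whole-scalp throughout

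*SAP*

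**What the plan says.** The SAP paragraph on whole-scalp treatment (section 5.2.7) defines the subset as "all subjects who indicated on the End of Blinded Treatment page of the eCRF that the whole scalp is treated twice per day". It gives no start date, no minimum time on the regimen and no link to what the subject was told at baseline. On the model it says: "The primary efficacy analysis of the percent change in SALT score will be repeated in this subset". The output is Table 14.2.11.3.

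The protocol shows that the instruction changed during the study. Its amendment history records: "Protocol Version 6.0 dated 08AUG2018 was amended to change the area of the study medication application". Version 7.0 is labelled Amendment 6, so this is Amendment 5. The synopsis adds: "Prior to amendment 5, subjects were instructed to treat patches of active alopecia areata and not the entire scalp".

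Protocol 7.3.1 deals with those already enrolled: "Subjects who signed the ICF prior to amendment 5 and do not consent to twice-daily applications to the entire scalp may continue in the study". It continues: "These subjects should be given the option to apply the study medication to the entire scalp at night only", with patches by day, or else patches plus a margin twice daily. The treated area has to be recorded ("The areas being treated must be identified in the source documentation and the eCRF as", followed by three categories), but no recording times are given. The SAP does not use this record to define the subset or to date a switch.

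**The concern.** Protocol 3.1 explains the move to the whole scalp: treating only visible patches might undertreat the disease. Table 14.2.11.3 is the only listed efficacy table restricted to the newer regimen, so readers will use it to judge that regimen.

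An end-of-treatment definition raises two problems for subjects randomised before the amendment.

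- **Dilution.** A subject may have spent most of the 24 weeks on patches and still be labelled whole-scalp.
- **Selection.** The decision to change comes after randomisation, when the subject can already see regrowth or irritation. If the drug influences either, membership can differ between arms and the comparison is no longer purely randomised.

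**Working it through.** **1. The plan's own figure.** Inputs from SAP 3.1: 40 per arm, difference 24, SD 38; two-sided alpha 0.05 from SAP section 5.

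- Standard error = 38 × √(2/40) = 8.50.
- Power = Φ(24/8.50 − 1.96) = Φ(0.86) = 0.806. A noncentral t with 78 df gives 0.797.

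The stated 80% reproduces. The documents give no size or power for the subset.

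**2. When membership is decided.**

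| Subject | Instruction at first application | What decides membership |
|---|---|---|
| Consented under Amendment 5 or later | Whole scalp twice daily | Mainly the protocol instruction |
| Randomised before Amendment 5 | Patches | A choice made after randomisation |

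The rule excludes no one for switching late.

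**3. What the model does with a late switcher.** SAP 5.2.2 lists treatment, visit, SALT group and treatment-by-SALT-group, with compound symmetry. There is no treatment-by-visit term, so the treatment contrast is common to Weeks 4, 8, 12, 16, 20 and 24. A subject who changes just after the Week 20 visit supplies five patch-only visits and one whole-scalp visit, so 5/6 = 83% of that subject's data come from the other regimen.

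Dilution can only be illustrated. If a share s of the subset switched late and carries half the effect (both assumptions), the expected difference is (1 − s) × 24 + s × 12:

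- s = 0: 24
- s = 0.1: 21.6 + 1.2 = 22.8
- s = 0.3: 16.8 + 3.6 = 20.4

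**4. Selection alone, by simulation.** Assumptions: SD 38; correlation 0.7 between interim and final regrowth; half the effect present at the interim point; 80% of pre-amendment subjects with interim regrowth below 10 points switch, against 30% of the others.

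| Consented before amendment (assumed) | Subset difference, true effect 24 | In subset, vehicle / active | Subset difference, true effect 0 |
|---|---|---|---|
| 25% | 23.9 | 90.0% / 88.5% | 0.0 |
| 50% | 23.8 | 80.1% / 76.9% | 0.0 |
| 75% | 23.5 | 70.2% / 65.5% | −0.1 (simulation error) |

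Steeper assumed switching on Week 12 response (80–90% of non-responders, 10–20% of responders) gave 23.0 and 22.7 with 50% enrolled before the amendment, and 22.1 and 21.2 with 70%. Across both sets the loss runs from 0.1 to 2.8 points. The largest is 2.8/8.50 = 0.33 of the full-trial standard error.

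**5. Cost of a consent-based subset.** If 50–70% enrolled before the amendment (assumption), 40 × 0.5 = 20 down to 40 × 0.3 = 12 per arm remain. Detectable difference = (1.960 + 0.842) × standard error.

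| Per arm | Standard error | Power for 24 points | Detectable at 80% power |
|---|---|---|---|
| 40 | 8.50 | 0.81 | 23.8 |
| 20 | 12.02 | 0.51 | 33.7 |
| 12 | 15.51 | 0.34 | 43.5 |

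**The case against.** The strongest reply is about size. What prompted the change was an amendment and a re-consent, not a response visit, so response-driven switching is conjecture and no late switcher is reported. Choices were made under blind, so with no drug effect nothing pushes the arms apart; in these simulations any bias is toward a smaller effect. This is one supportive table, and the significance rule rests on the ITT analysis. The remedy also costs more than the selection bias it removes: a standard error of 12.0 to 15.5 against 8.5 for the full trial, to recover 3 points or fewer. It drops subjects who changed early and used the whole scalp for most of the period.

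All of that stands as a limit on magnitude. It does not repair the definition: the rule allows switching at any time, and the result cannot be tied to one regimen.

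A reader might infer more than the documents support:

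- **That a whole-scalp subject who cuts back for an application-site reaction drops out of the subset.** Protocol 7.6 allows only a short once-daily spell (6 days in total) before the Medical Monitor must review it, and Protocol 7.3.1 has no category for whole scalp once daily alone. The eCRF page is not available, so reclassification is not shown.
- **That randomisation is broken or false positives are inflated.** The simulations show no bias under no effect, and membership gaps of 1.5 to 4.7 percentage points in the tabulated set.
- **That treated area on Day 1 is on file.** Protocol 7.3 records the volume applied at baseline; 7.3.1 gives no timing for the area record.
- **That SALT group plainly belongs in this model.** SAP 3.3.1 says: "The strata will not be used in the subset analyses". The instruction to repeat the primary analysis leaves the wording unclear, but only a clarification is needed.

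**Conclusion.** The concern holds for the definition. For subjects randomised before Amendment 5, membership is decided after randomisation, and time on patches before a switch is counted as whole-scalp. The consequence is possible dilution and, only if the drug affects response or tolerability, a modest imbalance between arms.

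The illustrated selection bias is about 0 to 3 points on an assumed 24, and nil under no drug effect. The dilution figures (24 down to 20.4) rest entirely on an assumed share of late switchers and an assumed half effect. Neither the subset size nor the number or timing of switches is documented. The effect is confined to Table 14.2.11.3. This is a worthwhile, inexpensive improvement to a supportive analysis, not a threat to the trial's main conclusion.

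**What to change.** In SAP 5.2.7, before unblinding:

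1. Define the main whole-scalp subset by a pre-randomisation attribute: subjects who first consented under Amendment 5 or later, when whole scalp twice daily was the instruction. Analyse them as randomised, whatever they later applied.
2. Keep the end-of-treatment subset, labelled descriptive and non-randomised. Report its size by arm and, where the treated-area record allows, the number and timing of switches.
3. State how subjects who terminate early are classified in the end-of-treatment subset; the SAP is silent.
4. Reconcile SAP 3.3.1 with 5.2.7 so that it is clear whether SALT group is in this model.

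The cost is a few sentences and one more table. Consent date is already an SAP variable (it is used for age and days on study). The version signed should be confirmed from it and from when each site adopted the amendment.

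The statistical price is the loss of precision shown in the working, so the table should be read as an estimate with a wide interval. The consent-based subset also gives no clean comparison with earlier enrolees, because entry criteria changed at nearly the same time: adolescents became eligible in Version 7.0, dated two days after Version 6.0.
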